Part C: Consists of a screening period, treatment period, extension treatment period, and follow-up period.

Screening Period: Same as Part B.

Treatment Period: Eligible patients will enter a 6-month (24-week) treatment period. Group A will be dosed once every 4 weeks for a total of 6 doses; Group B will be dosed once every 6 weeks for a total of 4 doses; Group C will be dosed once every 8 weeks for a total of 3 doses. Specific dosing details are provided in the dosage and administration section. Patients will complete efficacy and safety assessments per the visit schedule, along with PK/PD blood sample collection.

Extension Treatment Period: After completing the treatment period, subjects will enter an extension treatment period of up to 6 months (24 weeks). Group A will be dosed once every 4 weeks for up to 6 additional doses; Group B will be dosed once every 6 weeks for up to 4 additional doses; Group C will be dosed once every 8 weeks for up to 3 additional doses. Patients will complete efficacy and safety assessments per the visit schedule, along with PK/PD blood sample collection.

Follow-up Period: At 84 days after the last dose/early withdrawal, safety assessments including vital signs, physical examination, laboratory tests (including complete blood count, urinalysis, and blood biochemistry), coagulation function, FDP, 12-lead ECG, anti-SR604 antibodies (ADA), and neutralizing antibodies will be performed. Bleeding events and their treatment, adverse events, and concomitant medications/treatments will be recorded. If safety evaluation parameters are abnormal, follow-up must continue until values return to normal, are deemed not clinically significant, are stable, or return to baseline.

Pharmacokinetics/Pharmacodynamics (PK/PD)

Biological Sample Collection:

All subjects participating in this trial will have biological samples collected at designated timepoints for PK/PD analysis, following the initially proposed sampling schedule. During the trial, based on the PK/PD data and analysis results obtained from completed dose cohorts, the PK/PD biological sample collection timepoints for subjects in subsequent dose cohorts may be appropriately adjusted as necessary.

Biological sample collection will be performed by authorized or trained medical personnel according to the requirements of the testing laboratory.

Table 8-2 PK/PD Sampling Timepoints and Time Windows (Part A)

Collection Timepoint	PK Sample	PD Sample	Tolerance Window

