※Note: Collected based on actual dosing duration. Added PD parameter: pro-inflammatory cytokines (IL-1beta, IL-6, TNF-alpha). If duplicate blood collection timepoints occur, collect only once

Collected blood samples will be centrifuged and stored frozen at –60°C or below. Test samples will be transported by a specialized cold chain logistics company to the central laboratory for analysis. Backup samples will be stored frozen at –60°C or below at the clinical trial institution or transported by a specialized cold chain logistics company to a sponsor-designated third party after trial completion.

Biological Sample Analysis:

All PK/PD biological samples collected from subjects will be transported to the central laboratory. Specific requirements will be executed according to the relevant standard operating procedures and testing requirements established by the central laboratory.

Safety and Immunogenicity Evaluation Parameters

Safety parameters: Incidence of AEs/SAEs/AESIs assessed through clinical signs and symptoms, vital signs, physical examination, laboratory tests (complete blood count, urinalysis, and blood biochemistry), coagulation function [PT, TT, INR, FIB, APTT, D-dimer], FDP, 12-lead ECG, injection site reactions, hypersensitivity/allergic reactions, thrombotic events, etc.; incidence of drug-related AEs/SAEs/AESIs; number and incidence of subjects with anti-drug antibodies (ADA) and neutralizing antibodies.

Immunogenicity parameters: Number and incidence of subjects with anti-drug antibodies (ADA) and neutralizing antibodies.

Efficacy Parameters (Part B)

Primary efficacy parameters:

At 12 weeks and 24 weeks of treatment, treatment-based annualized bleeding rate (ABR).

The ABR at 12 weeks of treatment can be calculated using the following formula: Total number of treated bleeding episodes from first dose to within 14 days after the 6th dose / $[(\text{date of 6th dose} - \text{date of first dose} + 14) / 365.25]$. The ABR at 24 weeks of treatment can be calculated using the following formula: Total number of treated bleeding episodes from first dose to within 14 days after the last dose / $[(\text{date of last dose} - \text{date of first dose} + 14) / 365.25]$.

Note: Total bleeding includes spontaneous and traumatic bleeding. A treated bleeding episode refers to a bleeding event for which factor replacement or bypassing agent therapy was administered.

Secondary efficacy parameters:

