1. At 12 weeks and 24 weeks of treatment, treatment-based annualized spontaneous bleeding rate;
2. At 12 weeks and 24 weeks of treatment, treatment-based annualized total joint bleeding rate (AJBR);
3. At 12 weeks and 24 weeks of treatment, treatment-based annualized menorrhagia bleeding rate (applicable only to female patients of childbearing age with menstruation who have congenital coagulation Factor VII deficiency);
4. At 12 weeks and 24 weeks of treatment, change from baseline in the Hemophilia Joint Health Score (HJHS) (Hemophilia A and B patients);
5. At 12 weeks and 24 weeks of treatment, change from baseline in the EuroQol-5 Dimension-5 Level (EQ-5D-5L) questionnaire.

Efficacy Parameters (Part C)

Primary efficacy parameters:

At 24 weeks of treatment and during the treatment period (including treatment and extension treatment periods), treatment-based annualized bleeding rate (ABR).

The following formulas can be used for calculation:

ABR at 24 weeks = (Number of treated bleeding episodes within the dosing interval after the last dose during the 24-week treatment period x 365.25) / (Date of last dose during the 24-week treatment period - Date of first dose + dosing interval)

ABR during the treatment period (including treatment period and extension treatment period) = (Number of treated bleeding episodes within the dosing interval after the last dose x 365.25) / (Date of last dose - Date of first dose + dosing interval)

Note: Total bleeding includes spontaneous and traumatic bleeding. A treated bleeding episode refers to a bleeding event for which factor replacement or bypassing agent therapy was administered.

The 'dosing interval' for the Q4W group is 28 days; for Q6W it is 42 days; for Q8W it is 56 days.

Secondary efficacy parameters:

1. At 24 weeks of treatment and during the treatment period (including treatment and extension treatment periods), treatment-based annualized spontaneous bleeding rate;
2. At 24 weeks of treatment and during the treatment period (including treatment and extension treatment periods), treatment-based annualized total joint bleeding rate (AJBR);
3. At 24 weeks of treatment and during the treatment period (including treatment and extension treatment periods), treatment-based annualized menorrhagia bleeding rate (applicable only to female patients of childbearing age with menstruation who have congenital coagulation Factor VII deficiency);

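### The ABR denominators add a full dosing interval after the last dose even when bleed observation ends sooner, and the Part B 12-week formula has no value without a 6th dose

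*Protocol*

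**What the plan says.** Under Efficacy Parameters (Part C), the 24-week ABR has the denominator "Date of last dose during the 24-week treatment period - Date of first dose + dosing interval". The ABR over treatment plus extension uses "Date of last dose - Date of first dose + dosing interval". The added interval is a constant for each group: "The 'dosing interval' for the Q4W group is 28 days; for Q6W it is 42 days; for Q8W it is 56 days".

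Under Efficacy Parameters (Part B), the 12-week ABR counts "Total number of treated bleeding episodes from first dose to within 14 days after the 6th dose" and divides by the time from first to 6th dose plus 14 days. The 24-week ABR counts "Total number of treated bleeding episodes from first dose to within 14 days after the last dose" and divides by the time from first to last dose plus 14 days.

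None of the four formulas refers to withdrawal or to the last bleeding record. Yet Trial Procedures foresees subjects leaving early. The Part C follow-up text reads "At 84 days after the last dose/early withdrawal, safety assessments", and Part B sampling runs to D211 or early withdrawal. Bleeding events are recorded at both of these visits.

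**The concern.** A rate is events divided by time under observation. If a subject leaves the trial partway through the interval after the last dose received, the rest of that interval is still credited as exposure. No bleed could have been recorded in it, so the subject's ABR is too low.

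The credit grows with the dosing interval: up to 28 days in Q4W, 42 in Q6W and 56 in Q8W. Part C randomises dosing frequency at a single dose level, so the error is tied to the one factor that differs between the groups. It makes the longer interval look better.

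The Part B 12-week formula has a different fault. It needs the date of the 6th dose, which a subject who stops after, say, dose 4 does not have. The adjacent 24-week formula, anchored on the last dose, does give that subject a value. The two formulas therefore treat the same early stopper differently, without explanation.

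**Working it through.** **Inputs.** Dosing intervals τ are 14 days (Part B) and 28, 42 and 56 days (Part C). Doses in the main period are 6 in 12 weeks for Part B (12 in 24 weeks) and 6, 4 and 3 in 24 weeks for Part C. There are 12 subjects per group. All come from Trial Design, Sample Size and Efficacy Parameters. No dropout rate is stated. The numerator is taken as all treated bleeds since the first dose. Read literally, the Part C numerator covers only the interval after the last dose; that is a separate wording problem.

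**1. Planned period.** For a subject dosed on schedule the denominator is (doses − 1) × τ + τ.
- Part C: 5×28+28 = 3×42+42 = 2×56+56 = 168 days.
- Part B: 5×14+14 = 84 days and 11×14+14 = 168 days.

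These equal 24, 12 and 24 weeks exactly, so the denominators are right for completers.

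**2. One subject.** Suppose bleed observation ends t days after the k-th dose, with t < τ. Observed time is (k−1)τ + t and the formula gives kτ. So formula ABR / observed-time ABR = ((k−1)τ + t) / (kτ), which is below 1.
- Observation ends halfway through the interval after dose 1: 0.50 in any group. After dose 2: 0.75.
- Halfway after the last scheduled dose of the 24 weeks: Q4W 0.917, Q6W 0.875, Q8W 0.833, Part B 24-week 0.958.
- Q8W, leaving 10 days after dose 2 with 2 treated bleeds: 2×365.25/112 = 6.52 by the formula, 2×365.25/66 = 11.07 on observed time.
- Near the extreme, one bleed and exit at day 14: 365.25/14 = 26.1 on observed time, against 365.25/28 = 13.0 (Q4W), 365.25/42 = 8.7 (Q6W) and 365.25/56 = 6.5 (Q8W).

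Since 56 is a multiple of 28, the Q8W denominator is never shorter than the Q4W one for any given exit day.

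**3. Average among withdrawers only.** Assume exit times uniform over 168 days. With K scheduled doses the mean ratio is 1 − H_K/(2K), where H_K = 1 + 1/2 + … + 1/K. The pooled ratio is mean observed time, 84 days, over mean denominator, τ(K+1)/2.

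| Group | K | Mean per-subject ratio | Pooled ratio |
|---|---|---|---|
| Q4W | 6 | 1 − 2.450/12 = 0.80 | 84/98 = 0.86 |
| Q6W | 4 | 1 − 2.083/8 = 0.74 | 84/105 = 0.80 |
| Q8W | 3 | 1 − 1.833/6 = 0.69 | 84/112 = 0.75 |

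A simulation of one million exit times gave per-subject ratios of 0.796, 0.740 and 0.694. For Part B dosing over 168 days it gave 0.871.

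**4. Arm level.** Assume m = 1 to 3 of 12 subjects withdraw and bleed at the same rate as the others. The arm mean ABR is then understated by (m/12) × (1 − mean ratio).
- Q4W: 0.204/12 = 1.7% to 3×0.204/12 = 5.1%.
- Q6W: 0.260/12 = 2.2% to 3×0.260/12 = 6.5%.
- Q8W: 0.306/12 = 2.5% to 3×0.306/12 = 7.6%.

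The gap between Q8W and Q4W is about 0.8 to 2.5 percentage points.

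**5. Part B at 12 weeks.** With five or fewer doses there is no 6th-dose date and the expression cannot be evaluated. One such subject is 1/12 = 8% of a dose group.

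**The case against.** **The SAP may deal with it.** The formulas are worded permissively ("The ABR at 12 weeks of treatment can be calculated using the following formula"; "The following formulas can be used for calculation"), and the Protocol leaves detailed methods to an SAP that is not shown. That would answer a missing detail. Here the Protocol writes out the calculation of its primary endpoint and offers no other, and the written rule gives a wrong result for some subjects. The point stands, though the SAP could already contain the cap.

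**The fixed interval matches planned observation.** This is largely right. Part C schedules efficacy collection 28, 42 or 56 days after the last dose and follow-up to 84 days. A subject who stops dosing but stays in follow-up is observed for the whole credited interval. Only those whose bleed observation ends inside it are affected.

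**The effect is small.** For an arm with few withdrawals it is. A reader might take the 80%, 74% and 69%, or the two- to four-fold gap in the day-14 example, as arm-level bias. They are not: the first apply among withdrawers only and the second to one near-extreme subject.

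**Observed-time ABR is not the truth either.** If a bleed triggers exit, bleeds divided by time to exit is biased upward for that subject. This stands and shapes the fix. A reader might also infer that frequent bleeders will be the ones to leave, but nothing in the Protocol shows it.

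**Conclusion.** The point holds in limited form. The two Part C formulas and the Part B 24-week formula understate ABR for any subject whose bleed observation ends inside the interval after the last dose. The understatement is large for an early leaver and modest for an arm: about 2 to 8% with 1 to 3 of 12 withdrawing. It grows with the dosing interval and so favours Q8W over Q4W. The arm figures rest on an assumed number of withdrawals, uniform exit times and equal bleeding rates, and would be larger if withdrawers bled more.

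A reader might infer that the primary ABR as a whole is limited to completers. It is not. Only the Part B 12-week formula is undefined, and only for subjects without a 6th dose; the other three can be computed for every dosed subject. Nor does the Protocol say that a subject without a 6th dose is excluded from the primary analysis. It simply gives no rule.

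The formulas should be corrected. The effect is not large enough to call the design into question.

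**What to change.** - **At-risk period.** In each formula, end it at the earlier of last dose plus dosing interval and the end of bleed observation. Count treated bleeds from the first dose over exactly that period.
- **Part B, 12 weeks.** Replace the date of the 6th dose with the date of the last dose received up to the 6th.
- **Summary.** Report each arm mainly as total treated bleeds over total observed time, with per-subject ABR as supportive. Capped per-subject values from short exposures are more variable and can be biased upward if bleeding triggers exit.

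For Part C this is a wording change in the Protocol and SAP. It needs dosing, bleeding and withdrawal dates, which are routine data, and completers keep their 168 days.

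Part B costs more. Dose Selection and Rationale reports all 24 subjects enrolled and first dosed as of May 2025, and this version is dated 13 January 2026. A subject first dosed on 31 May 2025 would reach D211 on 27 December 2025 if on schedule. Part B dosing is therefore probably complete, with open-label data in hand. Document the Part B change as late, show results by both the current and the revised formulas, and state whether any subject lacked a 6th dose. If none did, the 12-week change makes no difference.
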